7.1.2 Medical history and concomitant diseases

A complete review of the patient's past medical history will be conducted. Any concomitant disease, whether considered relevant for the study or not by the Investigator, must be recorded in the CRF.

7.1.3 Vital signs

Vital signs will be assessed at baseline (between 1 and 2 hrs after starting NAC) and again at 2.5, 10 and 20hrs after starting NAC. This will be recorded in the Case Report Form (CRF). The following vital signs will be evaluated in a supine position after at least 5 minutes of rest: blood pressure- systolic and diastolic (mmHg), heart rate (BPM), respiration rate (/min), pulse oximetry, temperature (°C) and temperature route.

Height (estimated) and weight will be collected at baseline.

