Anaphylactoid reactions, characterised by symptoms such as rash, wheeze, and hypotension are thought to be dose and rate-related. Studies in Edinburgh have demonstrated that these are mediated by histamine release (Pakravan et al 2008). In one prospective randomised controlled study, the rate of anaphylactoid reactions was 18% (Kerr et al 2005). A recent prospective study of patients treated with the standard intravenous NAC regimen in the Edinburgh toxicology unit showed that around 15% developed anaphylactoid reactions (Pakravan 2008) and similar figures have been reported from Newcastle (Fathalla et al 2008). Anaphylactoid reactions are managed by interrupting the infusion temporarily and administering an antihistamine and bronchodilators. Most affected patients can be restarted on NAC at a lower infusion rate. Females, asthmatics and patients with low plasma APAP concentrations are at higher risk of anaphylactoid reactions (Schmidt et al 2001, Waring et al 2006, Pakravan 2008) and fatal adverse reactions have been reported, although these are rare.

Although highly effective, especially if started within a few hours of paracetamol overdose, the current licensed intravenous 20.25hr NAC regimen has several disadvantages. Firstly, intravenous NAC is commonly associated with adverse effects, the most common being nausea, vomiting and anaphylactoid reactions. Anaphylactoid reactions appear related to the rate of infusion of NAC and its concentration in blood. Thus they are most common during, or soon after, the initial high dose infusion. Secondly, the infusion schedule is complex, requiring prescription of three different infusions, and this contributes to a high risk of medication errors, which may have serious, potentially life-threatening, adverse outcomes. Thirdly, the required duration of the infusion regimen results in prolonged hospital stay, especially as patients with paracetamol overdose often present during the night (Thanacoody et al 2013).

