7 PATIENT ASSESSMENTS AND DATA COLLECTION

7.1 Description of Assessments

7.1.1 Blood Samples

NAC will be given to all patients arriving to the hospital according to the standard guidelines when paracetamol/acetaminophen overdose is suspected. All patients that arrive to the hospital before 24hrs after POD will be asked if they will participate in the study.

As part of routine clinical care all patients presenting to hospital following a paracetamol overdose will have the following blood tests on arrival to hospital or 4hrs after overdose (whichever is the longer time).

- S-APAP level in serum
- Urea, sodium, potassium and creatinine
- Liver function tests (LFTs) ALT, Bilirubin and ALP
- Clotting screen: INR and Prothrombin time (PT)
- Haemoglobin, White Blood Cells(WBC), Mean Cell Volume (MCV)

Immediately prior to administering PP100-01 a study specific blood sample will be collected (10mL split over serum and plasma) which will measure:

- ALT, bilirubin and alkaline phosphatase (ALP)
- Prothrombin time and INR
- Serum creatinine
- Biomarkers: CK18 and microRNA MiR122, GLDH, mitochondrial DNA and others
- PP100-01 levels

These measurements are part of the sub-study examining novel biomarkers.

As part of routine clinical care there will be blood sampling at 10 hrs and 20 hrs after starting NAC. The following are routinely measured:

- S-APAP level in serum
- Urea, sodium, potassium and creatinine
- Liver function tests (LFTs) ALT, Bilirubin and ALP
- Clotting screen: INR and Prothrombin time (PT)
- Haemoglobin, White Blood Cells(WBC), Mean Cell Volume (MCV)

At these 10hr and 20hr venepuncture episodes study specific blood samples will also be collected (at each time 10mL split over serum and plasma) which will measure:

- Biomarkers: CK18 and microRNA MiR122, GLDH, mitochondrial DNA and others
- PP100-01 levels

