7.1.7 Treatment Phase

Treatment will start with the first NAC bag of 100 mg/kg in 200 ml ("loading dose") at time point '0'. Immediately prior to PP100-01 a study specific blood sample will be collected (time 2hr).

PP100-01 treatment is administered intravenously as a bolus infusion over 5 minutes at the dose specified by the dosing cohort:

- Group A: PP100-01 (2 µmol/kg calmangafodipir) after the "loading" dose of NAC
- Group B: PP100-01 (5 µmol/kg calmangafodipir) after the "loading" dose of NAC
- Group C: PP100-01 (10 µmol/kg calmangafodipir) after the "loading" dose of NAC

All necessary precautions will be taken during administration of the study drug. The patient will be monitored with vital signs (Section 7.1.3). Observation and medical treatment for anaphylactic shock will, as a standard be requisite.

The 12hr NAC regime will be continued with the second dose: 200 mg/kg NAC in 1000 ml i.v. over 10 hr. As per routine clinical practice, there will be one blood sample taken 2 hrs before the end of the second NAC bag (the 10hr time-point) and a second blood sample taken 10h later (the 20hr time-point).

The following procedures should be performed during the treatment phase at time-points: baseline, 2hr, 10hr and 20hr (see study schedule, section 7.2 (Table 1)):

• ALT, bilirubin and alkaline phosphatase (ALP)

- Prothrombin time and INR
- Serum creatinine
- Biomarkers: CK18 and microRNA MiR122, GLDH, mitochondrial DNA and others
- PP100-01 level will be assessed at 2hr, 10hr and 20hr

Any rescue medication given will be recorded in the Case Report Form by routine clinical staff.

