7.1.11 Assessment timelines

2, 2.5 hour assessments should be performed +/-15mins of the timepoint. PP100-01 treatment should be +/- 10mins of timepoint. 10, 20 hour assessments should be performed +/-30minutes of the timepoint.

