9 DOSAGE AND ADMINISTRATION

9.1 Dosing Regime Acetylcysteine (NAC)

Standard NAC regimen:

300 mg/kg NAC IV (200 mg/mL) in 5% glucose (dextrose) or 0.9% Sodium chloride over 12hr: 100 mg/kg in 200 mL over 2 hr ("loading dose"), then 200 mg/kg in 1000 mL over 10hr. Note that for patients weighing more than 110 kg, the dose will be calculated using a 110 kg weight as per the TOXBASE guidance.

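### Baseline vital signs may precede the PP100-01 bolus by up to 70 minutes, during NAC loading, and the ±15-minute window for the 2 h blood conflicts with its required pre-dose order

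*Protocol*

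**What the plan says.** **Vital signs and ECG.** Protocol 7.1.3: "Vital signs will be assessed at baseline (between 1 and 2 hrs after starting NAC", then at 2.5, 10 and 20 h. The schedule in Protocol 7.2 puts this reading in a column labelled as pre-PP100-01 and has no vital signs at 2 h. Protocol 7.1.6 asks for a baseline ECG but gives no time for it. Protocol 7.1.7 relies on the 7.1.3 vital signs for monitoring around the bolus.

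**Treatment clock.** The NAC loading infusion is "100 mg/kg in 200 mL over 2 hr" (Protocol 9.1). The bolus is scheduled at 2 h. Protocol 7.1.11 allows: "PP100-01 treatment should be +/- 10mins of timepoint". The bolus itself lasts 5 minutes (Protocol 7.1.7).

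**Assessment windows.** Protocol 7.1.11 and the schedule footnote: "2, 2.5 hour assessments should be performed +/-15mins of the timepoint".

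**The 2 h blood.** Protocol 7.1.1: "Immediately prior to administering PP100-01 a study specific blood sample will be collected". Protocol 7.1.7 gives the same order and labels the sample as 2 h.

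**Analysis.** SAP 4.6 analyses vital signs by the methods of SAP 4.5: values at each time point, then change from baseline, each compared with NAC alone within cohort and pooled. SAP 4.2 lets baseline values come from any of three visits and does not say which visit serves which variable.

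**The concern.** Protocol 2.3 lists an immediate fall in blood pressure among the important potential risks of calmangafodipir that need close monitoring. To see such a fall in one patient, the reading before the bolus has to describe that patient's state just before the bolus. Here it may be over an hour old and taken partway through an infusion that can itself change blood pressure. A patient whose pressure dips on NAC, recovers and then falls after PP100-01 could show almost no change from baseline. A patient still reacting to NAC at baseline could show an apparent improvement.

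This reaches the primary outcome. Under Protocol 7.1.4, clinically significant changes in vital signs are recorded as adverse events and judged for relationship to study drug. SAP 4.4 tabulates relationship to NAC and to PP100-01 separately. The safety committee reviews each cohort of 8 before the next dose level opens.

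The 2 h blood is a different problem. Two sections place it before the bolus, but the numeric window is symmetric about 2 h. A check for deviations that used only the window would accept a post-dose sample. The 2 h PP100-01 level (SAP 4.3) and the first scheduled biomarker sample could then be pre-dose in one patient and post-dose in the next.

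**Working it through.** The plan states no figure for the interval between baseline and bolus, so there is none to reproduce. The check is interval arithmetic on the stated windows, in minutes after the start of NAC.

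| Event | Source | Window |
|---|---|---|
| NAC loading infusion | Protocol 9.1 | 0 to 120 |
| Baseline vital signs | Protocol 7.1.3 | 60 to 120 |
| PP100-01 bolus start | Protocol 7.1.11, 2 h ± 10 | 110 to 130 |
| 2 h assessments, including blood | Protocol 7.1.11, 2 h ± 15 | 105 to 135 |
| 2.5 h assessments | Protocol 7.1.11, 2.5 h ± 15 | 135 to 165 |

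1. **Baseline to bolus.** Longest gap: 130 − 60 = 70 min. With the bolus exactly at 120, the gap is 0 to 60 min. The windows alone would allow a baseline 120 − 110 = 10 min after the earliest bolus, but the schedule's column label rules that out.
2. **Baseline to the 2.5 h reading.** Shortest 135 − 120 = 15 min; longest 165 − 60 = 105 min.
3. **Bolus start to the 2.5 h reading.** 135 − 130 = 5 min to 165 − 110 = 55 min.
4. **2 h blood against bolus start, by the window alone.** Latest: 135 − 110 = 25 min after the start, or 20 min after a 5-minute bolus ends. Earliest: 130 − 105 = 25 min before.
5. **Bolus against the end of loading.** 120 − 110 = 10 min. The bolus window opens before the nominal end of the infusion that PP100-01 is said to follow.
6. **Precision of the comparison with NAC alone.** The 95% CI half-width for a difference in mean change, in SD units, is t(0.975, n₁+n₂−2) × √(1/n₁ + 1/n₂).
   - Within cohort, 6 v 2: 2.447 × √(1/6 + 1/2) = 2.00 SD.
   - Against pooled controls, 6 v 6: 2.228 × √(1/6 + 1/6) = 1.29 SD.
7. **Effect of one unrepresentative baseline.** An error of d mmHg moves the mean change by d/6 in a PP100-01 group and by d/2 in a cohort's two controls. The documents give no basis for a value of d.

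**The case against.** **The randomised control.** A reader might infer that the PP100-01 effect cannot be isolated at all. The documents do not support that. NAC-alone patients follow the same NAC clock and the same baseline rule, so the shared loading effect cancels in expectation. Even a baseline at 2 h would not isolate PP100-01 within an arm, because the second NAC infusion follows. This stands. What remains is timing noise, very small control groups, and possible differences in timing between arms, since allocation is open and made at screening, before the baseline reading.

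**Other safeguards.** Values at each time point are compared before change is analysed, so a low 2.5 h pressure shows whatever the baseline. Adverse events are also assessed at baseline, 2 h and 2.5 h (Protocol 7.1.9). Both points stand and limit the harm. Neither supplies a blood pressure taken just before the bolus.

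**The blood sample.** A reader might conclude that it is untied to the bolus, or that the ALT and INR baseline is compromised. Neither follows. A post-bolus sample would breach the explicit order in Protocol 7.1.1 and 7.1.7; the fault is a window not reconciled with that order. Protocol 7.1.7 lists baseline and 2 h separately, the schedule has screening bloods, and the protocol's 50% ALT rise is measured against admission. Experimental biomarkers are left to a separate plan (SAP 3.1).

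**NAC reactions.** Protocol 2.2.2 says of anaphylactoid reactions: "Thus they are most common during, or soon after, the initial high dose infusion". That passage describes the 20.25 h regimen, whose first dose runs over 15 minutes. Protocol 2.2.2 and 3.2 say the 12 h regimen reduces these reactions. The sentence therefore cannot be used for how often a baseline here would be disturbed.

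**Precision.** It is tempting to state how much a closer baseline would reduce the SD of change. The documents give no within-patient correlations, so no such figure is offered. With half-widths of 1.29 to 2.00 SD, sample size is the main limit on the group comparisons.

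**Conclusion.** The point holds as a modest design weakness plus one internal contradiction. The baseline reading can be up to 70 min older than the bolus, and the interval it spans to the 2.5 h reading varies sevenfold (15 to 105 min). Within-patient and within-arm change therefore mixes NAC-loading and PP100-01 effects. The group comparison with NAC alone is protected in expectation but imprecise. Individual causality judgements have no such protection. The ECG baseline is looser still, with no stated time.

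The ±15 min window contradicts the pre-dose order of the 2 h blood by up to 25 min. The consequence is confined to the 2 h drug level and the first biomarker sample.

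These figures assume that staff use the full stated windows; actual practice may be tighter. That the 2 h blood is not the ALT and INR baseline is inferred from the protocol, because the SAP does not name the baseline visit for each variable.

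**What to change.** - **Protocol 7.1.3, 7.1.6, 7.1.11 and both copies of the schedule:** take the existing baseline vital signs and ECG shortly before the bolus, for example within the preceding 15 min, and at the same clock time in NAC-alone patients (105 to 120 min if anchored to the nominal 2 h).
- **Protocol 7.1.11 and the schedule footnote:** reconcile with 7.1.1 and 7.1.7 by stating that the 2 h blood must precede the bolus, whatever the ±15 min window.
- **CRF:** record actual times of the baseline readings, the 2 h blood, the bolus and the 2.5 h readings.
- **SAP 4.2 and 4.6:** use these readings as the baseline for vital signs and ECG, and name the baseline visit for every other variable.
- **Bolus window:** reconcile the ±10 min allowance with the sections that place PP100-01 after the loading dose. This review takes no position on which should govern.

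With the 15-minute example, the longest baseline-to-bolus gap falls from 70 to 15 min. The baseline to 2.5 h span in PP100-01 patients becomes 135 − 130 = 5 min to 165 − (110 − 15) = 70 min. The remaining spread comes largely from the bolus and 2.5 h windows, so recording actual times still matters.

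The cost is a few minutes more work just before dosing, when staff are already present to draw blood, and a protocol amendment needing ethics, regulatory and local R&D approval (Protocol 16.1). No visit is added.

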Calmangafodipir (PledOx[®]) had a safety profile in this study as would be predicted by non-clinical data. The most common preferred terms for safety reporting in the study (more than 25 events reported in total) were: neurotoxicity, thrombocytopenia, fatigue, nausea, neutropenia, peripheral sensory neuropathy, diarrhea, leukopenia, decreased appetite, anemia, paresthesia, neuropathy peripheral, vomiting and pyrexia. As expected, the frequencies of neurotoxicity, thrombocytopenia and neutropenia that were reported as AEs mirrored the reporting of these symptoms as chemotherapy-induced toxicities analyzed as efficacy data. Grade 2 neurotoxicity occurred in a smaller proportion of patients in the 5 μ mol/kg PledOx[®] group (4.4%, 2 events) compared to placebo (16.7%, 16 events). No other apparent differences between the treatment groups in terms of adverse events.

To date, approximately 150 patients with mCRC received repetitive dosing with calmangafodipir (PledOx[®]). Approximately 240,000 patients have received single doses of the closely related compound mangafodipir at similar or higher doses. No new significant safety data have emerged during the treatment reporting period. Immediate blood pressure fall, severe diarrhoea and severe vomiting, have previously been identified as important potential risks, to be closely monitored as the clinical program progresses.

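### No scheduled, analysed blood-pressure reading falls between the PP100-01 bolus and the 2.5 h assessment (0 to 50 min after the bolus ends, nominally 25), although immediate blood pressure fall is a named risk

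*Protocol*

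**What the plan says.** Protocol 2.3, under clinical development, states: "Immediate blood pressure fall, severe diarrhoea and severe vomiting, have previously been identified as important potential risks, to be closely monitored". The sentence goes on to make clear that it concerns the clinical programme as a whole.

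Protocol 7.1.3 gives the schedule for this trial: vital signs at baseline, 1 to 2 h into NAC, and "again at 2.5, 10 and 20hrs after starting NAC". Both copies of the table of assessments (the synopsis and 7.2) agree with it. Vital signs are marked at baseline, 2.5, 10 and 20 h. The 2 h column carries the PP100-01 dose but no vital-signs mark.

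On administration, Protocol 7.1.7 says "PP100-01 treatment is administered intravenously as a bolus infusion over 5 minutes" and places the pre-dose blood sample at 2 h. It then says "The patient will be monitored with vital signs (Section 7.1.3", which refers back to the schedule above. The neighbouring sentences require precautions during administration and observation for anaphylactic shock.

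Protocol 7.1.11 sets the windows: "2, 2.5 hour assessments should be performed +/-15mins of the timepoint" and "PP100-01 treatment should be +/- 10mins of timepoint".

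SAP 4.6 summarises and analyses vital signs at their measurement time points, using the methods of SAP 4.5.

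**The concern.** Safety and tolerability is the primary objective, and blood pressure and pulse are listed secondary outcomes (Protocol 4). Protocol 13.1 describes the risks of PP100-01 given with NAC as unknown. An effect described as immediate is best measured close to the dose, yet the first scheduled post-dose reading is at 2.5 h and is timed from the start of NAC rather than from the bolus.

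Three consequences follow.

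- A fall that begins and resolves before the 2.5 h reading contributes nothing to SAP 4.6.
- Time since the bolus varies between compliant patients, so even the 2.5 h values are not measured at a common point after dosing.
- Any blood pressure taken between the bolus and 2.5 h is unscheduled. Staff know the allocation, so such readings may be taken more often in PP100-01 patients than in NAC-alone patients.

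The comparison with NAC alone matters here. Protocol 2.2.2 lists hypotension among the features of anaphylactoid reactions to NAC and says that, with the standard regimen, these reactions cluster during or soon after the initial infusion. The bolus follows directly on the NAC loading dose. A single low reading after the bolus cannot be attributed without a reading at the same clock time in control patients.

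**Working it through.** The documents state no gap between bolus and reading, so there is no figure of the plan's own to reproduce. The check is clock arithmetic in minutes after the start of NAC.

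**Inputs**

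| Item | Value | Source |
|---|---|---|
| Start of bolus | 120 ± 10 | Protocol 7.1.7, 7.1.11, 7.2 |
| Duration of bolus | 5 | Protocol 7.1.7 |
| First post-bolus vital signs | 150 ± 15 | Protocol 7.1.3, 7.1.11 |

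**Gap from end of bolus to reading**

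Gap = reading time − (bolus start + 5).

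- The bolus ends between 110 + 5 = 115 and 130 + 5 = 135.
- The reading falls between 150 − 15 = 135 and 150 + 15 = 165.
- Nominal gap: 150 − 125 = 25 min.
- Longest gap: 165 − 115 = 50 min.
- Shortest gap: 135 − 135 = 0 min.

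Two patients who both comply can therefore differ by 50 min in time since the bolus.

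**Outside the windows.** Protocol 9.3 allows an infusion to be interrupted for an anaphylactoid reaction. If that delayed the bolus to 150 min or later, a 2.5 h reading taken on the nominal clock would precede the drug. This would be a departure from the window and is not part of the 0 to 50 min range.

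**Illustration of what the 2.5 h reading would miss.** The documents give no duration for such a fall, so this part rests on assumptions. Suppose the fall has resolved by d minutes after the end of the bolus, and both times are uniform within their windows and independent. The reading misses the fall when the gap exceeds d:

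- for d from 0 to 20, P(miss) = 1 − d²/1200;
- for d from 20 to 30, P(miss) = 0.5 + (25 − d)/30;
- for d from 30 to 50, P(miss) = (50 − d)²/1200.

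| d (min) | P(miss) |
|---|---|
| 5 | 1 − 25/1200 = 0.98 |
| 10 | 1 − 100/1200 = 0.92 |
| 15 | 1 − 225/1200 = 0.81 |
| 20 | 1 − 400/1200 = 0.67 |
| 25 | 0.50 |
| 30 | 0.5 − 5/30 = 0.33 |
| 45 | 25/1200 = 0.02 |

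A simulation of one million pairs of times gave the same values. The 2.5 h reading is thus a poor detector of a fall lasting a few minutes and a good one for a fall lasting 45 minutes.

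**Other routes of capture.** Adverse events are assessed at 2 h and 2.5 h (Protocol 7.1.9). The investigator asks about them during the infusion (10.3). Clinically significant vital-sign changes are recorded as adverse events (7.1.4). Questioning finds symptoms and observation finds visible signs. A fall with neither needs a measurement, and none is scheduled in this interval.

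**The case against.** Much can be said on the other side, and part of it stands.

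- **A reader might infer that Protocol 2.3 and 7.1.3 contradict each other.** They do not, strictly. The statement in 2.3 is background about the programme and sets no reading or interval for this trial. What remains is a gap between a named risk and the measurement schedule.
- **A reader might infer that patients are unmonitored around the bolus.** The documents do not support that. Protocol 7.1.7 requires precautions and observation, 9.4 has a clinician supervise treatment, and adverse-event assessments fall on both sides of the bolus. The reference to 7.1.3 could also mean which signs to monitor rather than when. That reading is possible, but it still yields no stated reading time and no value for the scheduled analysis.
- **A reader might infer that dose escalation rests on the incomplete vital-signs tables.** It does not. Under Protocol 10.10 the safety committee reviews adverse-event and patient-safety data and any analyses it requests. The SAP covers the final report and publications.
- **Prior experience is reassuring.** Protocol 2.3 and 3.4 report no meaningful adverse-event differences from placebo at the same doses given over about 5 minutes, and 2.3 reports no cardiovascular effect in dogs at up to 31 times the highest dose. This lowers the expected frequency of a fall. It does not cover the combination with NAC in overdose patients, which Protocol 12.3 notes is untested.
- **The size of the problem is uncertain.** The miss probabilities depend on durations that the documents do not give, and a gap of 0 min is as compliant as one of 50 min.

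The case report form is not among the documents, so nothing can be said about which fields it holds. Only the schedule and the SAP can be cited.

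**Conclusion.** The point holds in a limited form. No scheduled, analysed blood-pressure reading falls between the bolus and the 2.5 h assessment. Within the allowed windows that assessment comes 0 to 50 min after the end of the bolus, nominally 25. The timing follows directly from the protocol. How often a fall would be missed depends on its duration, which is unknown.

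What is exposed is a brief, symptomless fall that nobody happens to measure. It would be absent from SAP 4.6, and unscheduled readings cannot replace the scheduled comparison because they may differ between open-label arms. Adverse events, the primary outcome, remain the main safety record and are not undermined by this.

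The change is worth making because it is cheap and the trial is about safety. It would not make the trial able to exclude such falls. With 6 PP100-01 patients per dose, even complete capture with no event leaves an exact 95% upper limit of 1 − 0.025^(1/6) = 0.459, or about 46%. The gain is a described, comparable measurement near the dose.

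**What to change.** 1. Reconcile Protocol 2.3, 7.1.3, 7.1.7 and both copies of the table of assessments, so that it is clear what vital-signs measurement, if any, is intended around the bolus and whether the reference to 7.1.3 concerns the signs or the times.
2. As a data-collection change, add to the table of assessments a recorded outcome reading of blood pressure and pulse, timed from the actual end of the bolus. Take a reading at the matching clock time in NAC-alone patients. Record the actual times of the bolus and of the reading.
3. In SAP 4.6, summarise the change from baseline at this reading by treatment group, alongside the existing time points.

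The exact timing of the reading, and the response to any fall, are clinical decisions for the clinical team. Nothing here proposes a monitoring or treatment rule.

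Cost: one or more extra non-invasive cuff readings per inpatient, and minor wording in the protocol, case report form and SAP.
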